## 1 PROTOCOL SUMMARY

### 1.1 SYNOPSIS

Title:	ADDRESSING SOCIAL ISOLATION, LONELINESS, AND ELEVATED SUICIDE RISK AMONG VULNERABLE OLDER ADULTS THROUGH AN 8 WEEK CARING CONTACTS TREATMENT: A PARTIALLY NESTED RANDOMIZED CONTROLLED TRIAL
Grant Number:	90INNU0021-03-00
Study Description:	
This PN-RCT evaluates an 8-week caring contacts treatment that is delivered to older adults (urban racially diverse, suburban, and/or rural) in 20-30 minute warm calling "dosages", over 3 conditions. Conditions include 2 treatment (i.e. treatment provided by helpers trained in a standardized and manualized Belongingness and Empathy training grounded in narrative reminiscence and the befriending literature (BE), and treatment provided by helpers trained in BE plus a standardized, manualized, and evidence-based suicide intervention training, the Aging Variant of LivingWorks ASIST (BE WITH), and 1 control (no treatment). Hypotheses include: (a) participants in the BE and BE WITH treatment conditions will experience significantly more improvement across measures than those in the control condition over the course of the 8-week treatment and (b) outcome improvements for those in treatment conditions will be more pronounced for those who begin the period at greater risk.

Objectives * :	
Primary Objective: To develop BE WITH Innovation and equip the Aging Services Network (ASN) with proven skills to reduce social isolation, loneliness, and elevated suicidality and promote social support/well-being with older adults receiving nutrition services.
 
Secondary Objectives: To validate and replicate BE WITH

Endpoints * :	
Primary Endpoint: Reduction in social isolation, loneliness, and elevated suicidality and improved social support/well-being for older adult participants receiving nutrition services.
 
Secondary Endpoints: Improved frequency of empathic and suicide intervention best practice behaviors by trained volunteers

Study Population:	Target $n = 540$ to adequately power the PN-RCT; men and women, aged 65 or older, receiving nutrition services, without instance of dementia or cognitive impairment, and in the state in the Southeastern US.
Description of Sites/Facilities Enrolling Participants:	There will be three Area Agencies on Aging, and 25 senior centers that will be involved in this clinical trial.

**Description of Study  
Intervention/Experimental  

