## 4. 3 OBJECTIVES AND ENDPOINTS

Objective	Metric/Variable	Hypothesis/role/endpoint	Analysis
-----------	-----------------	--------------------------	----------

Validate the BE WITH innovation	Reduce loneliness, and elevated suicidality, and increase the degree to which social needs are met	Over the 8-week treatment loneliness and suicide desire (as measured by the UCLA loneliness scale, Interpersonal Needs Questionnaire) will be significantly decreased, and the variable of social needs being met (as measured by the social provisions scale) will be increased for both treatment groups	Longitudinal growth modeling
Validate the BE WITH innovation	Three treatment conditions	Those older adult participants randomly assigned to the BE or BE WITH treatment condition will demonstrate significant improvements in mental health outcomes when compared with the control group	Longitudinal growth modeling
Validate the BE WITH innovation	Risk tier	Those older adults that start the 8-week treatment at medium or high risk will have statistically significant improvements when compared with those of low risk	Longitudinal growth modeling
Validate the BE WITH innovation	Provider effects	Determine if there is variance in outcomes as a result of the provider assigned. 60 providers were trained in either BE or BE WITH and carried caseloads of older adult clients enabling the nesting of effects to determine if there are individual or group level provider effects	Multilevel modeling
Validate the BE WITH innovation	Improved quality, frequency of empathic and suicide intervention best practice behaviors by trained NS providers	An augmented version of Gould's (2013) coding protocol was developed to quantitatively behaviorally code treatment call dosages.	independent quantitative behavioral coding, double coding, 2 protocols, inter-rater agreement, coefficient kappas

The main overarching objective of the clinical trial is to validate the 8-week BE WITH warm calling program, equipping the Aging Services Network (ASN) with proven skills to reduce social isolation, loneliness, and elevated suicidality, while also promoting social support/well-being. The goal of the validation objective is to garner the evidence needed to get the first such program on the National Council on Aging's Evidence Based Registry.

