### 2. 9.2 SAMPLE SIZE DETERMINATION

To determine appropriate sample sizes, we used formulas developed for PN-RCTs with continuous outcomes and binary outcomes as well as results from a closely related study that tested the effect of the ASIST intervention with similar outcome measures. To detect an effect size of .40 with a continuous outcome, utilizing a Type I error rate of .05, power of .80, ICC of .20, and R^2 of .50 (for baseline covariate), we need 270 older adults with 30 volunteers each calling 6 older adults. For a binary outcome under the same assumptions, we would require 414-522 older adults with 46-58 volunteers for most estimates of the probability of an outcome in the treatment and control groups. Recruiting 540 older

adults (180 in each condition) and 60 volunteers (30 for each treatment condition) provides an adequate sample to evaluate major effects of interest in all proposed analyses.

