### 4. 9.4 STATISTICAL ANALYSES

#### 1. 9.4.1 GENERAL APPROACH

For descriptive statistics, categorical and continuous data will be presented percentages, means with standard deviations, and ranges. For qualitative research, procedural and interpretive rigor will be monitored and maintained with the use of particular CQR methodology such as Consensual Qualitative Research paired with odds ratio analysis to ensure that there are no demographic or treatment confounders. For inferential tests, we will use p-value at .01 and confidence intervals for statistical significance, along with effect sizes, etc. Covariates and confounders are pre-specified in the sections below. Checks of assumptions (e.g., normality) underlying statistical procedures will be performed and any corrective procedures needed and recommended by our biostatistician will be applied.

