Since the clinical trial is structured to occur in cohorts, the longitudinal multilevel modeling (growth modeling) analysis will be run after each cohort is completed. Despite early cohorts being underpowered, we find significant value in understanding if the data are trending in the expected directions, and/or if there are any issues that need to be addressed. The methodologist running the analysis will remain unblinded throughout the analysis process. There are no temporary suspension or safety findings that would prompt temporary suspension of the treatment. The frequency of monitoring the end points is daily as older adult participants are on a rolling recruitment and finishing their treatment at different points in time. There is no effect of the interim analysis on the final analysis as it is the same analysis. Type I error results when running many different types of tests, however we are running the main analysis with an underpowered sample so that we are learning and understanding as we go. The final analysis will be the same code just with all the participants across all 4 cohorts.

---

7. 9.4.7 SUB-GROUP ANALYSES

Sub-group analyses on the primary endpoints will be assessed in two ways: (a) multi-level modeling by treatment severity group (same primary analysis, conducted independently for low, medium, and high risk patients), and (b) cluster analysis to explore any potential differential treatment effects across predefined patient subgroups (e.g., age, sex, race, etc.). Interaction terms between any subgroup variables (i.e. age, sex, baseline severity) and treatment condition will be included to assess whether the trajectory of outcomes over time varied by subgroup. This approach will enable the examination of both between- and within-patient variability while accounting for repeated measures and clustering.

Since the secondary endpoints are serving as a fidelity check (i.e. trained helpers increased skills, retained skills, etc.) and were are only planning for approximately 60 trained helpers, which would be under powered, any differences in sub-groups, we imagine will be challenging to detect. Despite this,

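### Hypothesis (b), larger benefit at higher risk, has no designated test: Section 9.4.7 plans a severity-by-treatment interaction, which can test it, beside separate per-tier fits, which cannot, and does not say which decides.

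*Combined protocol and SAP*

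**What the plan says.** Hypothesis (b) in the Synopsis (1.1) is that "outcome improvements for those in treatment conditions will be more pronounced for those who begin the period at greater risk". The risk-tier row of the table in Section 3 restates it: those who start "at medium or high risk will have statistically significant improvements when compared with those of low risk". The analysis named there is only longitudinal growth modelling.

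Section 9.4.7 gives two analyses that bear on this:

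- Route (a) is multilevel modelling by severity group: "same primary analysis, conducted independently for low, medium, and high risk patients".
- The same paragraph adds: "Interaction terms between any subgroup variables (i.e. age, sex, baseline severity) and treatment condition will be included". The stated purpose is to see whether outcome trajectories differ by subgroup.

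No section says which of these decides (b), or what follows if they disagree. Baseline severity is not defined as the tier or as a score. Two significance levels appear. Section 9.4.1 says "we will use p-value at .01 and confidence intervals for statistical significance", while Section 9.2 sizes the trial "utilizing a Type I error rate of .05, power of .80, ICC of .20". The number of tiers is also unsettled. Sections 3, 4.1 and 9.4.7 use low, medium and high tiers, but Section 8.1 enrols only middle- and high-risk people and makes low-risk people ineligible.

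**The concern.** A claim that benefit is larger in one tier than another needs an estimate of the difference between the tiers' treatment effects, with its standard error. Fitting the model separately in each tier gives two or three effects and p-values but no such estimate. Each tier holds only part of the sample, so one tier can reach significance and another miss it when the true effects are identical.

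Route (a) is the only planned analysis that names the three tiers, and Section 3 words the hypothesis in terms of statistical significance. If the two routes disagree, the plan gives no rule for choosing. A stated hypothesis could then be reported as supported, or a tier described as not benefiting, on a pattern that chance produces often. Who benefits matters for the national roll-out that Section 2.3.3 has in view.

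**Working it through.** **Inputs from the documents.** d = .40, ICC = .20, R² = .50 for the baseline covariate, planning alpha .05 and power .80 (9.2); 180 people per arm and 30 callers per called arm (9.2); caseload 5-7 (6.1.2), taken as 6; alpha .01 for inferential tests (9.4.1).

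**Assumptions.** Two-sided tests; equal tier sizes; each caller's caseload spread evenly over the tiers; no attrition; one called arm versus control; one post-treatment score adjusted for baseline. R² is applied either at both levels or within callers only, which gives the ranges below.

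**Reproducing the plan's figure.** Section 9.2 says: "To detect an effect size of .40 with a continuous outcome", and, with R² "of .50 (for baseline covariate), we need 270 older adults with 30 volunteers each calling 6 older adults". I read this as 15 callers and 90 people in each called arm plus 90 controls. With J callers of m people and n controls, and R² at both levels,

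V = [ICC(1−R²) + (1−ICC)(1−R²)/m]/J + (1−R²)/n.

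For J = 15: V = (0.10 + 0.40/6)/15 + 0.50/90 = 0.01667, SE = 0.129. A noncentral t with 14 df gives power .82. J = 14 gives .79. So 15 callers per arm, 30 callers and 270 people in all, is reproduced.

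**Per-tier precision in the 540 design.** Here J = 30. The term ICC(1−R²) is 0.10 with R² at both levels and 0.20 with R² within callers only. Shared callers make tier estimates covary by C = 0.10/30 = 0.00333 or 0.20/30 = 0.00667.

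- Three tiers (m = 2, n = 60): V = (0.10 + 0.20)/30 + 0.50/60 = 0.01833, SE .135; or (0.20 + 0.20)/30 + 0.50/60 = 0.02167, SE .147.
- Two tiers (m = 3, n = 90): V = (0.10 + 0.133)/30 + 0.50/90 = 0.01333, SE .115; or (0.20 + 0.133)/30 + 0.50/90 = 0.01667, SE .129.

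**Same true d = .40 in every tier.** Results come from 400,000 multivariate normal draws with these variances and covariances:

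| Tiers | Alpha | Power per tier | Tiers disagree on significance | Lowest tier not significant, a higher tier significant |
|---|---|---|---|---|
| 3 | .01 | .56-.65 | 59-61% | 28-29% |
| 3 | .05 | .78-.84 | 37-43% | 15-19% |
| 2 | .01 | .70-.81 | 26-32% | 13-16% |
| 2 | .05 | .87-.93 | 11-18% | 6-9% |

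The last column is the pattern that could be taken as support for (b). If the highest tier itself must be significant, the three-tier figure falls to about 20% at .01 and 12-15% at .05.

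**Interaction test, same equal effects.** For the difference between two tiers, variance = 2(V − C): 0.030 (SE .173) with three tiers and 0.020 (SE .141) with two, under either R² reading. It rejects in 1% or 5% of trials, of which half are in the direction of (b).

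**Interaction power at two-sided .01** (critical value 2.576):

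- True difference .2: .2/.173 = 1.15, power 8%; .2/.141 = 1.41, power 12%.
- True difference .4: .4/.173 = 2.31, power 40%; .4/.141 = 2.83, power 60%.

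**The case against.** The strongest reply is that the right test is already planned. Section 9.4.7 lists baseline severity among the treatment interactions, and Section 3 words the hypothesis as a comparison with low risk. No section says that tier p-values will be compared or will decide (b). On a natural reading, the interaction tests the difference and the separate fits describe each tier. This stands in part. A reader might infer that the plan has no test of differential benefit, or that it commits to judging (b) by tier p-values. The documents support neither. What remains is that the interaction is not named as decisive, and that the only analysis naming the tiers has no between-tier test.

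A reader might also take the rate at which tiers disagree, up to about 60%, as the rate of false support for (b). It is not. It includes patterns that contradict (b), it reaches that level only with three equal tiers at .01, and it is 11-18% with two tiers at .05.

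Two further limits stand. Sections 3 and 9.4.6 specify growth modelling over repeated occasions. That would change per-tier precision, and the documents give no inputs for it. Equal tiers and callers shared across tiers are also assumptions.

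**Conclusion.** The point holds as a missing designation together with a tier-by-tier method that cannot answer the hypothesis. Under equal true effects of d = .40, reading (b) from tier-specific significance would show an apparently supportive pattern in about 28-29% (.01) or 15-19% (.05) of trials with three tiers, and 13-16% or 6-9% with two. The interaction test errs in 1% or 5%. These are figures for one scale and one called arm, under the assumptions listed in the check. They show the order of size and do not predict the growth model's behaviour. The main comparison of called arms with control is not affected.

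The tier conflict bears directly on this. If the eligibility rule in Section 8.1 governs, there is no low tier, the three-tier figures do not apply, and the contrast with low risk in Section 3 cannot be estimated.

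**What to change.** In Section 9.4.7, name the already planned interaction as the only test of hypothesis (b), and specify:

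- treatment by tier (by time, in the growth model), as a pre-specified contrast of higher with lower risk in the hypothesised direction;
- each called arm versus control;
- one named outcome, since Section 9.1 lists many, and one stated alpha, resolving .05 against .01;
- one model on all randomised participants, with tier main effects and the planned caller structure.

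Report tier-specific effects with confidence intervals from that same model, as descriptive results, in place of the independently fitted tier models. Make no within-tier significance claims. Reconcile Section 8.1 with Sections 3, 4.1 and 9.4.7 on whether a low tier exists.

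The cost is wording and one joint model in place of two or three; no new data are needed. The drawback to disclose is low power: at two-sided .01, roughly 8-12% for a between-tier difference of .2 and 40-60% for .4, under the same assumptions. The plan should therefore state that a non-significant interaction does not show equal benefit across tiers.

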#### 10.1.1.2 CONSENT PROCEDURES AND DOCUMENTATION

Informed consent will be administered over the phone to potential older adult participants. If they consent, older adult participants will be provided the baseline measure set, and informed that they will be subsequently contacted after they are assigned a treatment condition. After scoring their measures, and weighted stratified random assignment, participants will be mailed a participation plan. A member of the research team will also go over the details regarding their participation with them over the phone during the call back.

2.

#### 10.1.2 STUDY DISCONTINUATION AND CLOSURE

This study may be temporarily suspended or prematurely terminated if there is sufficient reasonable cause. Written notification, documenting the reason for study suspension or termination, will be provided by the suspending or terminating party to study participants, investigator, funding agency, and regulatory authorities. If the study is prematurely terminated or suspended, the Principal Investigator (PI) will promptly inform study participants, the Institutional Review Board (IRB), and sponsor/funding agency and will provide the reason(s) for the termination or suspension. Study participants will be contacted, as applicable, and be informed of changes to study schedule.

Circumstances that may warrant termination or suspension include, but are not limited to:

- Determination of unexpected, significant, or unacceptable risk to participants
- Insufficient compliance of study staff to the protocol
- Determination that the primary endpoint has been met
- Determination of futility
- The funding that has been secured is cut early and abruptly

The study may resume once concerns about safety, protocol compliance, and data quality are addressed, and satisfy the funding agency, sponsor, IRB, or other relevant regulatory or oversight bodies.

---

### 3. 10.1.3 CONFIDENTIALITY AND PRIVACY

All records will be kept private to the extent allowed by law. The following people will have access to identifiable information:

- [name] and [name]
- Institutional Review Board
- The Administration for Community Living (part of the Federal Department of Health and Human Services)

We will use two different codes to ensure we de-identify you from your data. The first is a numeric code that is assigned to you, and the second is a code generated from a combination of your initials and county both de-identify you on project records to protect your confidentiality. The information gathered from the calls will be stored on a password-protected and firewall-protected computer. The key that holds your code will be stored separately from the data to protect your privacy. The audio recordings and any transcripts will be destroyed within 5 years of completing the study, along with the code key information. Since any information that is sent over the internet may not be secure, we are only using data encrypted protocols and are not logging IP addresses. Also, only the case managers at the participating agency will know that you have elected to participate. That person will not have any access to any of your data and will not even know which group you have been assigned to.

---

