## 2. 6.3 MEASURES TO MINIMIZE BIAS: RANDOMIZATION AND BLINDING

We will use weighted stratified random assignment. After participants are baselined, we will score their data and assign them a risk tier (low, medium, high). Subsequently, we will randomize them to one of 3 conditions: BE condition, BE + ASIST condition, or control. Since the trial is being conducted in cohorts (waves), and to ensure the least amount of time between being baselined and starting the treatment, participants will be randomized one by one after they are baselined. The weighted component enables there to be equal representation of both risk tier and number of participants across all 3 treatment conditions within the confines of the ongoing nature of the trial.

At the time of baseline, participants are assigned 2 codes: one that is fully numeric, and another that is alphanumeric. The PI and graduate student(s) will have access to the unblinded data (i.e. both the older adults' names, codes, and baseline data) as the PI is supervising the process and a few graduate students will be helping with scoring, and the weighted stratified random assignment. The methodologist will only have access to the participants' codes and raw data. They will remain blind to ensure the most objective analysis of the data.

If a participant remains at elevated risk for suicide at the conclusion of the treatment, we will unblind them and report to their assigned case manager.

We will also use separate documents with participant codes only to track the following: treatment condition, rebaselines, any survey/measurement issues, risk tiers, etc. to ensure an additional level of rigor in protecting against any bias. Further, in all tracking files that the PI's research lab utilizes, only participant IDs will be utilized (i.e. tracking which participants are up for the next measurement occasion, etc.).

The only potential inadvertent unblinding that we could foresee would be with respect to the use of the Friendlybuzz system. The treatment providers do need to know the first names of the older adult participants, therefore ONLY their first names will be available. The data team, however, is completely distinct from the treatment team, and will not have access to the Friendlybuzz system.

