**Health and Wellbeing**

3. Generalized Anxiety Disorder (GAD-7) measures anxiety.

[https://adaa.org/sites/default/files/GAD-7\\_Anxiety-updated\\_0.pdf](https://adaa.org/sites/default/files/GAD-7_Anxiety-updated_0.pdf)

4. Patient Health Questionnaire (PHQ-9) measures depression.

[https://med.stanford.edu/fastlab/research/imapp/msrs/\\_jcr\\_content/main/accordion/accordion\\_content3/download\\_256324296/file.res/PHQ9%20id%20date%2008.03.pdf](https://med.stanford.edu/fastlab/research/imapp/msrs/_jcr_content/main/accordion/accordion_content3/download_256324296/file.res/PHQ9%20id%20date%2008.03.pdf)

5. Short Form Health Survey (SF-12) measures quality of life.

<https://www.hoagorthopedicinstitute.com/documents/content/SF12form.pdf>

6. Interpersonal Needs Questionnaire (INQ-15) measures suicide desire. The team will be using the thwarted belongingness scale only due to results from previous study.

<https://psy.fsu.edu/~joinerlab/measures/INQ-15.pdf>

7. Session rating scale measures the quality of the therapeutic alliance between a counselor and a client. This scale was adapted from a clinical context to assess the alliance between the older adult client and the volunteer/provider.

<https://www.uvm.edu/~cpincus/Session%20Rating%20Scale.pdf>

Measure	Acronym	What it measures	When to measure	Reliability/ Validity	Number of items	Sponsor (ACL) Category

University of California, Los Angeles Loneliness Scale	UCLA	Loneliness	All time points	Cronbach's alpha: 0.72  Discriminant validity and convergent validity demonstrated	3 items	Category 2: Socialization
Generalized Anxiety Disorder	GAD-7	Anxiety	All time points	Cronbach's alpha: 0.92  Good criterion, construct, factorial and procedural validity demonstrated	7 items	Category 3: Health and Well-being
Patient Health Questionnaire	PHQ-9	Depression	All time points	Cronbach's alpha: 0.89  Good concurrent validity when compared with SRQ-20 (71%, $p < 0.001$ ) and construct validity demonstrated	10 items	Category 3: Health and Well-being
Social Provisions Scale	SPS-5	Social Needs Being Met	All time points	Cronbach's alpha: 0.88  Criterion-related and structural validity demonstrated	5 items	Category 2: Socialization
Short Form Health Survey	SF-12	Quality of Life	All time points	Reliability: test-retest correlation of 0.76 for 12-item Mental Component Summary (MCS)	12 items	Category 3: Health and Well-being

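### Section 10.1.3 says the agency case manager gets none of the participant's data, with no suicide-risk exception, yet 6.3, 8.2 and 8.3.5 require persistent suicide risk to be reported to the assigned case manager

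*Combined protocol and SAP*

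**What the plan says.** Section 10.1.3 (Confidentiality and Privacy) addresses the reader as 'you'. It opens with a general assurance, "All records will be kept private to the extent allowed by law", and then lists who may see identifiable information: two named individuals, the IRB and the federal funder. Case managers are not on that list. They appear at the end of the section, where "only the case managers at the participating agency will know that you have elected to participate". The next sentence says of the case manager "That person will not have any access to any of your data", and adds that this person "will not even know which group you have been assigned to".

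Three other sections provide for a report to a case manager:

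- Section 6.3 covers the end of treatment: "If a participant remains at elevated risk for suicide at the conclusion of the treatment", then "we will unblind them and report to their assigned case manager".
- Section 8.2 says that when risk stays heightened over time, the PI and research team will tell the senior center case manager assigned to the participant.
- Section 8.3.5 makes sustained suicide risk the one exception to its rule that adverse events are not reported beyond the study team and database. It sends that report to the assigned case managers and says the agreements with the participating counties record this.

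Section 10.1.3 neither repeats this exception nor refers to it.

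**The concern.** The confidentiality section gives a blanket assurance about one recipient, and the safety sections name that recipient for one of the most sensitive findings the study can produce. According to 8.3.5, the county agreements record the exception. The section whose wording faces the participant does not.

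Two things are at stake. The protocol's own account of confidentiality should be true for every participant, including those who are reported. And a staff member who took 10.1.3 literally could hesitate over a suicide-risk report that the protocol rightly wants made. The matter is one of consistency and disclosure, not of statistical inference.

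**Working it through.** No arithmetic applies. The check is whether the sections can be read together, and whether anything in the supplied text reconciles them.

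1. **Is the reporting optional?** No. Sections 6.3, 8.2 and 8.3.5 all state it as something that will be done. The triggers differ slightly (end of treatment in 6.3, risk over time in 8.2, sustained risk in 8.3.5), but all three send the report to a case manager.

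2. **Is it the same case manager?** Section 10.1.3 places the person at the participating agency, 8.2 at the senior center, and 6.3 and 8.3.5 say only that the person is assigned to the participant. These most likely describe one role. If they do not, the report would also reveal participation to somebody else, which 10.1.3 excludes by saying that only the agency case managers will know of it.

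3. **Is what is reported part of the participant's data?** For 8.2 this is well supported. That section speaks of meeting risk criteria for suicide desire, and the measures list in 8.1 says "Interpersonal Needs Questionnaire (INQ-15) measures suicide desire" (the team uses its thwarted-belongingness scale). Section 6.3 does not say how end-of-treatment risk is determined. Section 8.3.5 treats sustained risk as an adverse event, and 8.3.4 allows such events to surface either in data collection or in treatment calls. So derivation from questionnaire answers is shown for 8.2 only. In all three sections, however, the report concerns an identified individual's risk status learned through the study, and 10.1.3 speaks of 'any' data.

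4. **Does anything in 10.1.3 carve out the report?** The only qualifier is the reference to what the law allows. It concerns legal limits on privacy and gives no notice that the study itself plans a disclosure. The access list does not help either, since case managers are absent from it.

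5. **What does 'unblind' in 6.3 pass on?** The section does not say. Earlier in 6.3, the PI and graduate students "will have access to the unblinded data (i.e. both the older adults' names, codes, and baseline data", so there the word covers identity and baseline data rather than the assigned arm. Linking the code to the name is the likely meaning.

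6. **How many people are affected?** Only those reported. The documents give no rate of sustained or end-of-treatment risk. The figure in 6.1.1 of roughly 20% at risk of suicide refers to older adults receiving home and community-based services generally and is not such a rate. No number is therefore derived.

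**The case against.** The strongest defence is a narrow reading of 'access'. Section 10.1.3 uses that word for data and 'know' for group assignment. The safety sections speak of reporting or communicating a status. None of them gives the case manager scores, files, recordings or codes. On this reading staff could raise the alert while granting no access to data, so a reader who infers that the two texts can never both be honoured goes further than the wording allows. That much stands. The narrow reading is still not the natural one for a lay participant told that a person will have no access to any of their data, and the companion clause about group assignment suggests that the passage concerns what the case manager learns.

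A reader might also infer that participants are being misled. The documents do not show it. Section 10.1.1.2 says consent is given by phone, but the consent pages were removed before review and may already state the exception. The 'you' wording suggests text carried over from a consent document. That is an inference, and nothing shows that 10.1.3 itself is given to participants.

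A third temptation is to read 6.3 as disclosing the treatment arm to the case manager, against the 10.1.3 assurance about group. The section's own use of the term points to identity, so arm disclosure is not supported.

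Finally, the working rule is clear: three sections agree, and 8.3.5 says the county agreements record it. A missed safety report is therefore unlikely. This limits the seriousness of the point but does not make the 10.1.3 sentence correct.

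**Conclusion.** The point holds as an inconsistency in the protocol text, and it should be fixed. Section 10.1.3 is wrong as written for any participant whose suicide risk is reported under 6.3, 8.2 or 8.3.5. One sentence is at fault, and three sections contradict it.

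The conclusion rests on two assumptions: that 'any of your data' includes an identified person's risk status, and that the case managers named in the four sections hold the same role. The first is the natural reading, though not the only possible one. If the second fails, the conflict moves to the preceding sentence of 10.1.3, about who may know of participation.

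Harm to participants is not established, the number affected is unknown, and no effect on sample size, power, error rates or the primary analysis follows.

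**What to change.** Keep the safety report unchanged. Add one sentence to 10.1.3, next to the statement about case managers: suicide risk that stays elevated during the study or at its end will be reported by name to the participant's assigned case manager. That wording covers the triggers in 6.3, 8.2 and 8.3.5. Check the phone consent script and, if it lacks the same exception, add it.

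Optionally, say in 6.3 that 'unblind' means linking the participant code to the name and does not include the assigned condition. This would keep 6.3 in line with the 10.1.3 assurance about group.

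The cost is one wording amendment, which under the Statement of Compliance needs IRB approval before it takes effect. If the consent script changes, the same statement requires a decision on whether people who have already consented must consent again. No change to the design, data collection or analysis is needed.
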